### f) Procedures Involved in the Human Research

All eligible subjects will undergo visits at screening, baseline (week 0), visit 8 hours after week 0, week 1, week 2, visit 8 hours after week 2, week 3, and week 4 (end of study). The parameters of study drug dosing are as follows: isradipine as utilized in this trial will be administered twice daily. Isradipine will be titrated as follows: baseline (week 0) 5 mg/day BID; Week 2 increase to 10 mg/day BID if 5 mg was well-tolerated. Dosing will be flexible based on side effects with a maximum=10 mg/day. If 5 mg cannot be tolerated, the subject will be discontinued. Dosing was based on package labeling for hypertension and prior studies in Parkinson's disease (Simuni et al. 2010).

	Protocol Title:	A Molecular Approach to Treat Cognition in Schizophrenia: Ca 2+ Channel Blockade
	Principal Investigator Name/Contact Info:	[name] [contact]
	Primary Contact Name/Contact Info:	[name] [REDACTED]
	Date Revised:	May 16, 2017
	Study Number:	HSM# 12-0031, GCO# 12-0679, GCO# 13-1987

Measures described in detail below:

Safety Outcome Measures

- The Side Effects Checklist (SEC; physician administered) and side effect self-report form – (all visits)
- Vital signs including blood pressure (standing/supine – all visits)
- Blood pressure check within 8 hours of first dose. Staff contact number will be given to subject in case there are any problems before the 8 hour BP check (week 0). An additional blood pressure check 8 hours after increased dosage (week 2).
- Electrocardiogram (ECG); chemistry panel and CBC via blood draw (approximately 2 TSP blood drawn); urinalysis (screening & week 4)
- Urine toxicology (screening)
- Urine pregnancy test for women of childbearing potential (baseline)
- Abnormal Involuntary Movement Scale (AIMS) and Simpson Angus Scale (SAS) (all visits)
- Beck Scale for Suicidal Ideation (SSI) and Columbia Suicide Severity Rating Scale (C-SSRS) (all visits)

Clinical/Symptom Measures

- Structured Clinical Interview for the DSM-IV (SCID-IV) (screening)
- Symptom rating scales including the Brief Psychiatric Rating Scale (BPRS), the Scale for the Assessment of Negative Symptoms (SANS), the Hamilton Rating Scale for Depression (HRSD), the Clinical Global Impression Scale (CGI), the Clinician Administered Rating Scale for Mania (CARS-M) (all visits)

Neurocognitive/Functional Measures

- MATRICS Consensus Cognitive Battery\* (baseline & week 4)

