Data from this study may be used in medical publications or presentations. The information will be de-identified so that individual subjects cannot be recognized and the information will no longer be considered PHI. The information that is collected for research will be analyzed for many years and it is not possible to know how long this analysis and follow-up will take. Therefore, participants are allowing access to this information indefinitely.

Subjects will only be identified with a numerical code in compliance with HIPAA regulations. Raw subject data will be secured in double locked physical control. Digitized raw data will be similarly de-identified using coding and will be secured on an MS SQL server with Windows integrated security.

	Protocol Title:	A Molecular Approach to Treat Cognition in Schizophrenia: Ca 2+ Channel Blockade
	Principal Investigator Name/Contact Info:	[name] [contact]
	Primary Contact Name/Contact Info	[name] [REDACTED]
	Date Revised:	May 16, 2017
	Study Number:	HSM# 12-0031, GCO# 12-0679, GCO# 13-1987

Data analysis plan is included below. All analyses will be based on an intent-to-treat sample of subjects who received at least one dose of isradipine. Since the missing values may be dependent on the observed outcomes, we assume the missing data mechanism to be missing at random, and hence a mixed models analysis will be used to assess the treatment effect of isradipine with fixed effects for week and first order autoregressive covariance structure to evaluate change over time for all of the primary outcome measures. Cognitive measures will be handled differently, as these will only be collected at two time points – if missing data are substantial (or a complete visit is missing), subjects' data will not/cannot be meaningfully analyzed.

*Primary Analyses* will test the following hypotheses based on our specific aims:

To determine the feasibility of 4 weeks of isradipine on cognitive outcomes in SZ.  
Hypothesis: We will successfully recruit up to 80 stable schizophrenia and schizoaffective patients

To determine the safety of 4 weeks of isradipine on cognitive outcomes in SZ.  
Hypothesis: The frequency of new or worsened side effects (clinician-rated; self-reported; lab-based) will not be significantly different from baseline to end of study visit.

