A Fisher exact test will compare time-points by frequencies of new or worsened (compared with baseline) side effect severity ratings – this will be done for all side effects assessed by the SEC.

Differences on laboratory measures (chemistry panel, etc.) will be tested using repeated measures ANCOVA (baseline and week 4) and changes in vital signs (specifically blood pressure) will be assessed using mixed model ANCOVA, to incorporate data at each weekly visit.

Differences on SAS and AIMS total scores will be examined by calculating the  $\tau$ -b rank correlation between score and week for each subject and comparing the distribution of these trend scores with the Conover-Salsburg rank test.

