### **j) Withdrawal of Subjects**

If they choose to consent to the study and are eligible to begin the trial, they will be closely monitored and will visit with the study coordinator and study physician. Side effects will be rated weekly at each visit using an adverse events checklist completed by a study physician. Subjects with an exacerbation of psychosis/depression/mania on a 2-point CGI-change score will be discontinued and treated appropriately by the study physician. Suicidal ideation will be assessed at each visit with the Beck (SSI) and the Columbia Suicide Severity Rating Scale (C-SSRS). Significant suicidal ideation will be addressed immediately using the standard clinical response at ISMMS (evaluation at the walk-in clinic/psychiatric emergency room for potential need to hospitalize). Subjects at risk for suicidal behavior will be discontinued. Subjects with any other clinical worsening as noted by study physician, and any instance of an SAE will be discontinued. In addition, subjects who exhibit any inability to follow the protocol will be discontinued and withdrawn from the study.

To ensure orderly termination from the study, the study physician would meet with the subject to discuss termination and discontinuation of medication. Safety measures would be collected and a follow-up visit by phone would be scheduled to further ensure safe discontinuation. Discontinuing isradipine does not require a taper. We will schedule an in-person visit if necessary after the follow-up visit by phone to address any remaining concerns the subject may have.

Subjects may withdraw from the study for any reason at any time by contacting the principal investigator or any of the research staff. It is also possible to withdraw permission for the use and disclosure of any protected information for research, but it must be done in writing to the principal investigator. In the event permission is withdrawn, information that was already collected may still be used if that information is necessary to complete the research study.

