Along with closely monitoring for symptom exacerbation, each visit with the study physician will entail a detailed side effect evaluation, which will include vital signs and a side effect checklist. The most common side effects of isradipine include hypotension, edema, headache, dizziness, palpitations, fatigue, flushing, and constipation. Patients will be educated about the potential for hypotension and its symptoms, and blood pressure and symptoms will be measured at every visit. If the patient develops clinically significant hypotension (e.g., systolic blood pressure equal to or less than 90 mm Hg or diastolic equal to or less than 60 mm Hg, or if they experience significant associated symptoms), or if at any point in the study subsequent to baseline there is a blood pressure drop of 20% or more from blood pressure at baseline, they will be discontinued from the study medication and excluded from the protocol. Rare side effects have also been reported including arrhythmias, syncope, severe hypotension or myocardial infarction. The informed consent process will alert subjects to these potential risks and close monitoring will ensure prompt response to any adverse effects with appropriate treatment and/or study discontinuation, as indicated.

Additional risks are minimal and involve the completion of questionnaires, interviews and paper-pencil/computerized tests. Some of the questions may be distressing to the individual and subjects will be told that they may refuse to answer any questions that they so choose. The testing procedure can sometimes cause fatigue but we will ensure plenty of resting periods during the session and will instruct subjects to notify staff if they would like an additional break. Pain and bruising may be associated with the blood draw for screening labs; however, a trained phlebotomist will perform the procedure to avoid any additional discomfort.

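### No rule carries the side effects of early discontinuers, or reactions that resolve early, into the baseline-to-week-4 side-effect comparison

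*Combined protocol and SAP*

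**What the plan says.** Section 5(h) of the combined protocol and SAP lists the safety hypothesis under its primary analyses. The frequency of new or worsened side effects (clinician-rated, self-reported and laboratory) "will not be significantly different from baseline to end of study visit". Section 5(f) fixes that visit in its schedule: "week 3, and week 4 (end of study").

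The test follows in section 5(h): "A Fisher exact test will compare time-points by frequencies of new or worsened (compared with baseline) side effect severity ratings". It is to be run for every item of the Side Effects Checklist (SEC). The time-points and the denominator are not named. Laboratory measures are analysed "using repeated measures ANCOVA (baseline and week 4"). Blood pressure "will be assessed using mixed model ANCOVA, to incorporate data at each weekly visit". The Simpson Angus Scale (SAS) and the Abnormal Involuntary Movement Scale (AIMS) are analysed through each patient's trend of score over weeks.

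Patients can leave before week 4 for reasons tied to safety:
- Section 5(f): "If 5 mg cannot be tolerated, the subject will be discontinued". Dosing is also flexible according to side effects.
- Section 6, for clinically significant hypotension or a fall in blood pressure of 20% or more: "they will be discontinued from the study medication and excluded from the protocol".
- Section 5(j): discontinuation for clinical worsening or any serious adverse event (SAE). On termination, "Safety measures would be collected and a follow-up visit by phone would be scheduled".

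The SEC and the self-report form are completed at all visits (section 5(f)), and section 5(i) has all adverse events recorded. The analysis set in section 5(h) is everyone with at least one dose.

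**The concern.** The hypothesis is read at a visit that patients with troublesome side effects may not reach. The protocol discontinues them because of the outcome being measured, so their absence at week 4 is informative. A reaction that appears in week 1 and settles, perhaps because dosing was adjusted, would also be absent from a week 4 frequency.

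The hypothesis is framed as no significant difference. A comparison that loses affected patients moves towards that result, and does so more strongly the worse the drug is tolerated. At stake is whether the trial's main statement on side effects describes everyone who was dosed or mainly those who completed 4 weeks.

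**Working it through.** The plan gives no event rate, discontinuation rate, alpha or power for this comparison, so there is no stated figure to reproduce. The first three steps compare the sections; the fourth is an illustration on assumed numbers.

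**1. Does any provision supply a value for a patient who left early?**
- *At-least-one-dose set (5(h)).* It defines who belongs to the sample. It gives no week 4 rating to a patient who has none.
- *Missing-at-random mixed model (5(h)).* It does not apply to a Fisher test on frequencies.
- *Time-points (5(h)).* If every visit is compared, an event rated at a scheduled visit appears in that visit's frequency, but each later visit counts only patients still present. No cumulative count per patient is defined.
- *Termination measures (5(j)).* They are collected, but are not listed or assigned to a time-point.

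**2. Which components are affected?** The SEC and self-report ratings are. Blood pressure, SAS and AIMS use repeated visits, so values seen before discontinuation can contribute. Laboratory tests are scheduled only at screening and week 4 (5(f)), so an early leaver may have no post-dose sample.

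**3. What is the baseline count?** A rating that is new or worse than baseline cannot occur at baseline. The baseline frequency is zero by definition, whatever the drug does.

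**4. Illustration.** Assumptions: all 80 patients (the maximum in section 5(c)) are dosed; two-sided alpha is 0.05; 4 to 16 patients (5% to 20%) discontinue with a given side effect; 2 of those remaining have it at week 4. The baseline count is 0/80.

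With a zero baseline count, the observed table has probability C(n, x)/C(80 + n, x). For 2/72 this is (72 × 71)/(152 × 151) = 5112/22952 = 0.2227. The opposite extreme, with both events at baseline, has the larger probability (80 × 79)/22952 = 0.275, so the two-sided p is 0.2227. When both groups have 80, the two extremes are equally likely and the value doubles.

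| Discontinued with event | Week 4 reading | p | Any-time count | p |
|---|---|---|---|---|
| 4 | 2/76 (2.6%) | 0.24 | 6/80 (7.5%) | 0.028 |
| 8 | 2/72 (2.8%) | 0.22 | 10/80 (12.5%) | 0.0014 |
| 12 | 2/68 (2.9%) | 0.21 | 14/80 (17.5%) | < 0.0001 |
| 16 | 2/64 (3.1%) | 0.20 | 18/80 (22.5%) | < 0.0001 |

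The week 4 column hardly moves while the any-time rate triples. The p-values show only that the counting rule can reverse the plan's own test; step 3 explains why that test should not be kept.

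The same effect can be expressed as power. Let the any-time rate be 15%, let a share q of affected patients leave before week 4, and let the rest still have the event then. The week 4 rate is 0.15(1 − q)/(1 − 0.15q). For q = 0.5 this is 0.075/0.925 = 8.1%, among 80 × 0.925 = 74 patients. By exact binomial enumeration, the chance that the Fisher test reaches p < 0.05 is 99% for q = 0, 73% for q = 0.5, 35% for q = 0.75 and 0% for q = 1.

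**The case against.** A reader might infer that the plan excludes discontinued patients' events, that transient reactions leave no trace, and that the safety result is therefore biased low. The documents do not support this. No section says such events are excluded. The hypothesis could describe the interval up to the end of study, the Fisher time-points could include earlier visits, and termination measures could serve as a leaver's last rating. Adverse events are recorded throughout and safety outcomes are summarised after every 5 completers (section 5(i)). Blood pressure, which has the most explicit stopping rule, is modelled over the weekly visits. Some removals, such as worsening psychosis, may not be SEC items at all.

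These points limit the claim to the SEC and self-report comparison, and to what the plan leaves undefined. They do not close the gap. Recording an event does not place it in the stated test, and a frequency at each visit still omits those who have left.

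There is also a fair objection to the remedy. In a single-arm trial, taking any worsening over six post-dose visits collects background complaints such as headache or fatigue. That stands as a cost. The illustration rests wholly on assumed counts and says nothing about the likely size of the effect.

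**Conclusion.** The concern holds as a gap in the definition of the side-effect measure. No rule brings the SEC and self-report events of early discontinuers, or reactions that resolved early, into the comparison. Under a literal week 4 reading, or visit-by-visit frequencies among those present, such events would be lost, and the loss favours no significant difference. The direction follows from the stopping rules, provided that some discontinuations accompany checklist events. The size cannot be derived from the documents. This should be fixed; confidence is medium, because the text admits more than one reading.

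**What to change.** Change the analysis text in section 5(h); no dose or stopping rule is touched.

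- **Primary safety measure.** For each SEC and self-report item, report the proportion of all patients with at least one dose who have any new or worsened rating, against the pre-dose baseline, at any post-dose visit or at the termination assessment in section 5(j). Give an exact confidence interval in place of a test against baseline.
- **Severity.** Report the worst post-baseline severity per item.
- **Separate outcome.** Report the proportion discontinued for side effects, hypotension or an SAE.
- **Week 4 frequency.** Keep it as secondary, with its denominator stated.
- **Laboratory measures.** State that the baseline-to-week-4 result describes only patients with a week 4 sample.

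The ratings are already scheduled at all visits. Section 5(j) does not list the termination measures, so the plan should say whether the SEC and self-report form are among them. The cost is that reported rates will be higher and will include some background complaints that a single arm cannot separate from drug effects.

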### c) Number of Subjects

Up to 80 stable schizophrenia and schizoaffective patients will be recruited from the Mount Sinai Health System Outpatient Departments, and community advertisements.

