### **i) Provisions to Monitor the Data to Ensure the Safety of subjects**

Safety monitoring will be done on a patient by patient basis by the PI and the study physician on weekly visits. Side effects will be monitored closely and all AEs recorded. To increase safety, a blood pressure check will be done within 8 hours of this first dose (baseline). Staff contact number will be given to subject before the first dose in case there are any problems before the 8 hour BP check. Additionally, a blood pressure check will be done within 8 hours of increasing the dosage (week 2).

	Protocol Title:	A Molecular Approach to Treat Cognition in Schizophrenia: Ca 2+ Channel Blockade
	Principal Investigator Name/Contact Info:	[name] [contact]
	Primary Contact Name/Contact Info:	[name] [REDACTED]
	Date Revised:	May 16, 2017
	Study Number:	HSM# 12-0031, GCO# 12-0679, GCO# 13-1987

The PI will summarize all safety related outcomes after each set of 5 patients have completed the study and discuss these results with study physicians. This monitoring will be applied sooner than 5 patients if indicated, or if a SAE or unanticipated event occurs. All SAEs will be reported to the IRB within 24 hours and documented as per protocol. In the case that there are safety concerns from the PI or the IRB, this will be addressed in an ongoing manner. Independent of any SAEs, a Data Safety Monitoring Plan will be submitted to the IRB after the first 15 participants have been enrolled.

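### The Fisher exact test for SEC side effects treats repeated ratings of the same subjects as independent groups, and on the baseline-to-end contrast its baseline cell is 0/n by definition

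*Combined protocol and SAP*

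**What the plan says.** The safety hypothesis in section 5(h) is that the frequency of new or worsened side effects "will not be significantly different from baseline to end of study visit". The test for SEC items follows: "A Fisher exact test will compare time-points by frequencies of new or worsened (compared with baseline) side effect severity ratings", and "this will be done for all side effects assessed by the SEC". The test sentence does not say which time-points are compared, and it does not mention pairing.

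Section 1 describes a 4-week open-label trial, and no control group appears anywhere in the documents. Section 5(f) lists "The Side Effects Checklist (SEC; physician administered) and side effect self-report form" for all visits. Section 5(j) adds: "Side effects will be rated weekly at each visit using an adverse events checklist completed by a study physician". The analysis set in 5(h) is stated as "All analyses will be based on an intent-to-treat sample of subjects who received at least one dose of isradipine". Section 5(c) sets the size: "Up to 80 stable schizophrenia and schizoaffective patients will be recruited". No alpha, expected side-effect rate or within-subject correlation is given.

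**The concern.** There are two faults, and which one applies depends on how the test sentence is read.

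- **Two post-baseline visits, or raw prevalence at two visits.** The same people contribute to both rows of the table. Fisher's test takes the rows as independent samples. With positive within-subject correlation it usually rejects too rarely.
- **Baseline to end of study, as in the hypothesis.** The outcome is defined relative to baseline, so the baseline count is zero whatever the drug does. The comparison is with a zero rate that ordinary fluctuation in complaints would exceed.

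This is the specific test given for SEC items under a hypothesis listed among the primary analyses, and that hypothesis predicts no significant difference. On the first reading a conservative test supports it by default. On the second, a non-significant result can sit beside an incidence whose upper limit is far from zero, while at larger n pure fluctuation can be flagged as harm. What is at stake is the study's safety conclusion. Subject protection does not depend on this test: section 5(i) says "Side effects will be monitored closely and all AEs recorded", and laboratory values, blood pressure, SAS and AIMS have their own analyses.

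**Working it through.** The documents give no figure to reproduce for this test. Inputs from the documents: a single arm, ratings of the same subjects at every visit, and a ceiling of 80 subjects. Assumptions: two-sided alpha 0.05, evaluable n from 20 to 80, and the rates and correlations shown below.

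**A. Baseline to end of study (0/n against k/n).** With a zero cell and equal rows, the two-sided Fisher p-value is

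p = 2 × C(n,k) / C(2n,k).

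For n=80 and k=5: 2 × (80·79·78·77·76)/(160·159·158·157·156) = 0.059. For k=6, p = 0.028. The last column below is the binomial probability of reaching the threshold when the true worsening rate is 10%. It does not depend on how many subjects improve.

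| n | smallest significant k | p at that k | p at k−1 | chance of a flag at 10% worsening |
|---|---|---|---|---|
| 20 | 5 | 0.047 | 0.106 | 4.3% |
| 40 | 6 | 0.026 | 0.055 | 21% |
| 60 | 6 | 0.027 | 0.057 | 56% |
| 80 | 6 | 0.028 | 0.059 | 82% |

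At n=30 the threshold is also 6.

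Exact (Clopper-Pearson) 95% intervals for results the test would call non-significant:

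- 5/80 = 6.3% (2.1% to 14.0%)
- 5/40 = 12.5% (4.2% to 26.8%)
- 4/20 = 20% (5.7% to 43.7%)
- zero events: upper limit 4.5% at n=80, 8.8% at n=40, 16.8% at n=20

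If ratings only fluctuate, with 10% worsening and 10% improving, the Fisher test at n=80 still flags 82% of the time. An exact sign test of worsened against improved flags 2.8%.

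McNemar's test on the same flag does not remove the structural zero. Its p-value is 2 × 0.5^k, which is 0.063 at k=5 and 0.031 at k=6, so the threshold at n=80 is still 6.

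**B. Two visits with paired ratings.** This is a full enumeration of correlated binary pairs at latent correlation 0.3, 0.5 and 0.7. Each cell gives the three values in that order.

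| Assumed rates | n | Fisher power | exact McNemar power |
|---|---|---|---|
| 20% vs 35% | 80 | 50%, 50%, 50% | 56%, 64%, 76% |
| 20% vs 35% | 40 | 22%, 20%, 18% | 27%, 31%, 38% |
| 10% vs 25% | 80 | 66%, 67%, 69% | 71%, 78%, 86% |
| 10% vs 25% | 40 | 32%, 31%, 28% | 35%, 39%, 45% |
| 10% vs 25% | 20 | 12%, 11%, 9% | 10%, 9%, 8% |

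With no true difference (20% vs 20%, n=80), Fisher's actual size is 1.9%, 1.1% and 0.4% against a nominal 5%. At n=20 pairing brings little or nothing: at 20% vs 35% both tests have power of 10% or less.

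**C. Limits of a paired test of net change.** The exact sign test needs 6 worsened with 0 improved (p=0.031), 8 with 1, or 10 with 2. With 10% worsening and 5% improving, its power is 13%, 9%, 5% and 0.5% at n=80, 60, 40 and 20. With 15% and 5% at n=80 it is 44%.

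**The case against.** The strongest defence is that the hypothesis just before the test does name baseline and end of study, so the time-points are not really open. On that contrast a flag for worsening is a legitimate treatment-emergent outcome. The p-value tracks the count, and the tabulated frequencies would be seen anyway. The error there can also run in the cautious direction, by flagging harmless fluctuation. A paired test of net change would detect worsening far less often than the planned test (13% against 82% at n=80 with 10% worsening and 5% improving).

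Much of this stands. The named contrast is the more natural reading, so part B describes an analysis the plan may never run, at assumed rates. Flagging worsening misleads only if it is read as net change. But the named contrast is exactly the one with the forced zero, so naming it does not rescue the test. The low power of a paired test is a reason to report incidence with an interval, not to test against a zero fixed by definition.

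It can also be said that 5(h) prescribes a mixed model for change over time in all primary outcome measures. That sentence is general; the specific rule for SEC items is the Fisher test, and it governs.

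**Conclusion.** The concern holds. The pairing and the 0/n baseline cell follow from the text alone and need no assumption. The thresholds of 6 worsened subjects (n=30 to 80) and 5 (n=20) need only alpha at two-sided 0.05. The flag rates, power and size figures rest on the assumed rates and correlations, and 80 is a ceiling, so smaller evaluable samples are plausible.

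The direction of error is not uniform. The test is conservative between post-baseline visits. On the named contrast it is insensitive at small n and open to flagging mere fluctuation at large n. In no case does non-significance support the statement that side effects did not increase. This should be fixed, though it affects one safety analysis and not the monitoring of subjects.

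**What to change.** 1. Name the time-points in the SEC test sentence, consistent with the hypothesis.
2. Make the main SEC result the incidence of new or worsened ratings per item in all dosed subjects, with exact 95% confidence intervals. State whether this counts any post-baseline visit or only the final one, and how a dosed subject with no post-baseline SEC rating is handled.
3. Base the safety conclusion on those estimates and intervals, not on the absence of significance.
4. If a test of change is kept, use a paired one (Wilcoxon signed-rank, or exact sign or McNemar) on the actual baseline and last on-treatment ratings, not on the baseline-relative flag. Say openly that last on-treatment may differ from the end-of-study visit. State that the test addresses net change, can be much less sensitive to worsening when some subjects improve, and does not replace the incidence and its interval.

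The cost is analysis-plan wording only, since the ratings are already collected at every visit. The drawback is the low power of any retained paired test, shown in part C of the working.

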### 1) Objectives:

In this project we propose to conduct a 4-week open label cognitive enhancement trial of isradipine in up to 80 stable outpatients with schizophrenia and schizoaffective disorder.

The primary aim of this study is to evaluate the effects of the calcium channel antagonist, isradipine on cognitive dysfunction in patients with schizophrenia and schizoaffective disorder. Incomplete treatment response is common. Cognitive impairment and negative symptoms persist in a majority of patients even when positive psychotic symptoms are well-controlled, and they account for a large proportion of the variance in explaining functional disability (Keefe et al. 2007). This has led to a focused effort to target the specific treatment of cognition in patients with schizophrenia (Green and Nuechterlein, 2004), with somewhat limited success to date.

Novel treatment options have been limited by an incomplete understanding of the biological etiology of schizophrenia; however, recent data from the field of genomics have provided insights into the molecular underpinnings of schizophrenia and its associated symptoms. The majority of genetic risk loci identified to date show trans-disorder effects, increasing susceptibility across a broad range of neuropsychiatric disorders including schizophrenia and bipolar disorder (Williams et al. 2011; Purcell 2009). One possible explanation for this overlap is that several of these genes are influencing risk via their effects on shared phenotypes such as neurocognitive dysfunction. One such example is a single nucleotide polymorphism (SNP; rs1006737) in the calcium channel gene, CACNA1C; initially associated with bipolar illness (Sklar et al. 2008; 2011; Ferreira et al 2008) but also linked with schizophrenia (Green et al. 2009; Nyegaard et al. 2010) and recurrent major depression (Green et al, 2009). The strength of

	Protocol Title:	A Molecular Approach to Treat Cognition in Schizophrenia: Ca 2+ Channel Blockade
	Principal Investigator Name/Contact Info:	[name] [contact]
	Primary Contact Name/Contact Info:	[name] [REDACTED]
	Date Revised:	May 16, 2017
	Study Number:	HSM# 12-0031, GCO# 12-0679, GCO# 13-1987

the association signal for CACNA1C in major mental illness is unambiguous and several subsequent studies have evaluated the effects of CACNA1C variation on neurocognitive capacity.

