### d) Study Timelines

The recruitment and enrollment process will be active for approximately 24 months. The anticipated final date for this study is 7/2017. The patients will be informed of the length of the study, which will include 8 visits in total. There will be a screening visit, baseline visit when they will receive the study medication, a visit eight hours after the first dose of medication is taken (baseline) where blood pressure will be checked, 4 weeks of medication administration and weekly monitoring, and a visit eight hours after the dosage of the medication is increased (week 2) where blood pressure will be checked. They will be informed of all of the study procedures for each week, including assessments and medical tests.

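### Side-effect events are counted only as worse than baseline, so nothing shows how often they arise without isradipine, although a screening rating that could supply that rate is already scheduled

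*Combined protocol and SAP*

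**What the plan says.** Section 1 describes a "4-week open label cognitive enhancement trial of isradipine in up to 80 stable outpatients", so there is no concurrent control.

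**Schedule.** Section 5f states "All eligible subjects will undergo visits at screening, baseline (week 0), visit 8 hours after week 0", then weekly visits to week 4 with a further 8-hour visit after week 2. Among the safety measures it lists "SEC; physician administered) and side effect self-report form – (all visits". Section 5d describes a "baseline visit when they will receive the study medication". The SEC is therefore rated twice before isradipine, at screening and at baseline. That the baseline rating comes before the first dose is implied, not stated.

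**Analysis.** Section 5h makes safety a primary hypothesis: the frequency of new or worsened side effects should not differ significantly between baseline and the final visit. The SEC event is defined by "new or worsened (compared with baseline) side effect severity ratings", and a Fisher exact test compares time-points for every SEC item. The time-points are not listed. Blood pressure has a mixed model over the weekly visits. SAS and AIMS have a per-patient rank correlation of score with week. No analysis names the screening value of any of these measures.

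**The concern.** An event defined as worse than baseline counts change in one direction. A complaint absent at baseline and present at week 4 is an event, while one that resolves offsets nothing. The count at baseline must be zero, so a comparison of the final visit with baseline sets some number out of N against none out of N. Any background fluctuation pushes that comparison towards a signal, and a single arm offers no other estimate of the background.

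Section 6 says "The most common side effects of isradipine include hypotension, edema, headache, dizziness, palpitations, fatigue, flushing, and constipation". Several of these, such as headache and fatigue, are non-specific complaints. If the SEC asks about them, some worsening between two visits is plausible without isradipine. The primary safety result could then report a side effect where there is only visit-to-visit variation, with no means of telling the two apart.

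**Working it through.** The plan states no alpha, power, background rate or SEC item list, so it has no figure of its own to reproduce. Everything below rests on these assumptions: two-sided alpha 0.05; baseline is one of the Fisher time-points, as the hypothesis in section 5h indicates; N = 80 (the cap in section 1), with 60 and 40 for comparison; background worsening of 2%, 5% or 10% per item.

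**Step 1: how many patients give p < 0.05 against zero.** For k of N against 0 of N with equal N, the two-sided Fisher p-value is 2 × C(N,k) / C(2N,k).

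- N = 80, k = 5: p = 0.059.
- N = 80, k = 6: 2 × (80·79·78·77·76·75) / (160·159·158·157·156·155) = 2 × 0.01418 = 0.028.
- Six is also the smallest sufficient count at N = 60 (p = 0.027) and at N = 40 (p = 0.026).

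**Step 2: chance of six or more with no drug effect.** With X ~ Binomial(N, q), the chance is P(X ≥ 6).

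| Background rate q | N = 40 | N = 60 | N = 80 |
|---|---|---|---|
| 2% | <0.1% | 0.1% | 0.5% |
| 5% | 1.4% | 7.9% | 21% |
| 10% | 21% | 56% | 82% |

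These are per-item chances, and the test is repeated for every SEC item.

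**Step 3: does the screening rating help?** Binary ratings were simulated for 80 patients (4,000 runs) with no drug effect: a patient effect with SD 1, visit noise with SD 0.7, and a complaint present above a threshold of 1.6, 1.2 or 0.8. Three tests were compared. The first is the test against zero at baseline. The second is an exact McNemar test of week-4-versus-baseline worsening against baseline-versus-screening worsening. The third is the same McNemar test with worsening at any of four on-drug visits in place of week 4.

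| Worse at week 4 than baseline | Worse at any of four visits | False signals: against zero | Paired, one interval against one | Paired, any visit against one interval |
|---|---|---|---|---|
| 5.4% | 14.2% | 26% | 1.8% | 34% |
| 8.0% | 20.0% | 62% | 3.1% | 46% |
| 10.5% | 24.7% | 86% | 2.8% | 49% |

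The screening rating removes the problem only when one interval is set against one interval.

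**Step 4: do SAS and AIMS share the problem?** Per-patient tau-b over weeks 0 to 4 was simulated with stationary noise and no drug effect (80 patients, 300 runs). A one-sample Wilcoxon test stood in for the planned rank test, which needs a second group. Mean tau was about 0.00 and rejection about 6%. With selection on SAS ≤ 6 at screening, the results were 0.00 and 5%; with selection at baseline, 0.03 and 7%. Random fluctuation is not read as a trend.

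**The case against.** **Counting events against the pre-dose visit is an ordinary convention, and the missing untreated rate follows from the open-label single-arm design.** Both are true, and any resulting bias overstates harm. But the convention does not justify testing a count that is zero by definition, and here a second pre-dose rating exists.

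**The size is assumed.** This stands. The documents do not list the SEC items, and the list in section 6 describes isradipine, not the checklist. At a 2% background rate the false signal is negligible.

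**Screening is unmentioned, not excluded.** This also stands. If the Fisher test compared only on-drug visits with each other, the zero would not enter. There would still be no background rate, and the stated hypothesis would not be tested.

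**The screening-to-baseline interval is a weak reference.** Its length is not fixed. Section 5b requires residual-phase criteria at both screening and baseline, and section 5h analyses only dosed patients. Patients who worsen before dosing may drop out of the comparison, which would lower the untreated rate and make isradipine look worse. The interval is also free of isradipine, not of drugs, since antipsychotics continue.

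**Stronger readings.** A reader might infer that all the safety measures are compared with baseline alone, so that fluctuation biases them all. The documents do not support this: section 5h uses a mixed model for blood pressure and a trend over weeks for SAS and AIMS, where symmetric fluctuation averages out. A reader might also quote the chance that a patient has at least one worsened item, 1 − (1 − q)^k, which is 33% for 20 items at 2%. Section 5h tests each item separately, so that figure describes an endpoint the plan does not use.

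**Conclusion.** The point holds for the SEC analysis. The event is defined against baseline only, the single arm supplies no background rate, and the screening rating that could give one appears in no planned analysis. The per-item false-signal chance depends almost entirely on the unknown background rate and on N, so this is a risk that the plan leaves unmeasured, not a demonstrated error rate. It is worth fixing because the data are already scheduled and safety is a primary hypothesis. No claim is made that random fluctuation biases the blood-pressure, SAS or AIMS analyses. Systematic drift before dosing could affect them, but that is a separate matter.

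**What to change.** Amend the side-effect paragraph of section 5h as follows.

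1. For each SEC item, report the proportion new or worsened from screening to baseline beside the proportion new or worsened from baseline to each single on-drug visit, with week 4 as the main contrast.
2. Compare the two proportions within patient by a paired method, for example an exact McNemar test and a paired difference with a 95% interval. This replaces the Fisher test against baseline, which also treats repeated ratings of the same patients as independent.
3. Report the number of days in each interval.
4. Do not set worsening at any visit against the single untreated interval.
5. Optionally, enter screening as a second pre-dose point in the blood-pressure model, to show systematic drift before dosing.
6. State the limits: the untreated interval has no fixed length, and eligibility limits at screening and baseline may lower its rate. The result is a rough background rate and not a control arm.

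The cost is analysis wording and programming. No visit, measurement or patient is added.
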